3 INVESTIGATION PLAN

3.1 Study Design

3.2 This is a randomized open label trial that will compare the safety and efficacy of PA and AL in patients of both sexes between the ages of 3 months and 10 years who have symptomatic microscopically confirmed acute uncomplicated *Plasmodium falciparum* malaria. Patients will be randomized following a pre-generated randomization code. On the basis of the results of these assessments, the patients will be classified as having therapeutic failure (early or late) or adequate clinical and parasitological response (ACPR). The proportion of patients experiencing therapeutic failure during the follow-up period will be used to estimate the efficacy of the study drug(s). The primary outcome will be PCR-adjusted adequate clinical and parasitological response (ACPR) i.e., absence of patent parasitaemia, regardless of axillary temperature and without evidence of previous treatment failure up to day 28. Secondary outcomes will be adequate clinical and parasitological response without correction for reinfection, parasite clearance time, fever clearance time and the proportions of patients who are aphasitaemic or afebrile on days 1, 2, and 3.

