3.6.2 Exclusion criteria

- History of allergy to study drugs i.e. artemisinins, lumefantrine and pyronaridine
- Any concurrent illness that could hamper evaluation of response e.g. bacterial infections, viral infections, severe gastrointestinal disease, malnutrition (weight for height $<70\%$)
- Presence of clinical evidence of severe malaria such as prostration, inability to drink or breast feed, persistent vomiting, convulsion, severe anemia hemoglobin <5 g/dl), unarousable coma
- Patients with known chronic diseases like chronic kidney disease, chronic liver disease, malnutrition, cardiac failure, Sickle Cell haemoglobin (HbSS) etc.
- mixed or mono-infection with another Plasmodium species detected by microscopy;
- presence of severe malnutrition defined as a child aged between 6-60 months whose weight-for-height is below -3 z-score, or has symmetrical edema involving at least the feet or has a mid-upper arm circumference <115 mm)
- Parent or guardian who in the judgment of the investigator will not comply with protocol in the opinion of the investigator

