3.7 Sample Collection Procedure

Enrollees who have fulfilled the inclusion criteria would have the details of the study explained thoroughly to them. The parent or guardian will be required to sign an informed consent form once they agree to participate in the study. All enrollees will have a case record form (CRF). The CRF will be used to collect the following details.

1. Socio-demographic, clinical and laboratory details of all enrollees in the study. The CRF will also have the contact information of each enrollee as well as the past medical history.
2. Record details of each visit: These will include clinical details that would be assessed at each clinic visits, including physical examinations, blood film for malaria parasite, and hematocrit values for each enrollee. Any change in contact details or living situation would be noted.

For the enrollees, a medical history will be obtained from parent/guardian including presenting symptoms and current medications. Physical examination will be performed; weight and axillary temperature recorded. A finger prick blood sample will be obtained for thick blood smears and blood spots on filter paper for parasite genotyping. Five milliliters of venous blood sample will also be obtained for assessment of hematological and biochemical parameters.

Blood film for malaria parasite: Thick blood film will be prepared from finger prick sample of each enrollee at each contact time, stained with fresh 10% Giemsa stain at pH 7.2 and read under a light microscope at X1000 magnification. Gametocyte carriage will be specifically looked out for in the thick film on all contact days. Blood spots on filter paper will be obtained at enrollment and at follow up. This will be used for DNA analysis by polymerase chain reaction (PCR) to differentiate re-infection from recrudescence

Blood chemistry and hematology: 5mls of venous blood samples would be taken for clinical chemistry (electrolytes, urea and creatinine as well as a liver function test) evaluation at day 0 and on the follow up days.

Hematocrit measurement: This will be done by the micro-hematocrit method and the result recorded in percentage. The hematocrit will be done at enrolment and at each clinic visit.

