Enrollee will be withdrawn from the study if the parent/care giver withdraws consent, enrollee develop serious concomitant illness or report taking other unauthorized anti-malarial medication apart from the study drugs during the follow-up period. Those who withdraw consent will be revolved back to the hospital care while those who develop serious concomitant illness would have immediate medical care given to them and thereafter be referred for specialist care at Oni memorial children's hospital or University College Hospital, Ibadan at no cost to them. Enrollees who fail treatment with either of the two ACTs being evaluated will receive the alternative ACT under supervision.

Daily checks and corrections will be carried out on the CRF of enrollees seen to ensure correctness and accuracy. Blood samples collected from study participants will be transported to the respective laboratories in the University College Hospital Ibadan for analysis of blood chemistry and hematology parameters the same day they are collected. Efficacy parameters will be evaluated as follows:

- **Efficacy evaluation** will be based on WHO criteria of treatment outcome as follows; (1) Early treatment failure (ETF; danger signs or complicated malaria or failure to adequately respond to therapy on days 0–3); (2) Late clinical failure (LCF; danger signs or complicated malaria or fever and parasitemia on days 4–28 without previously meeting criteria for ETF or LPF); (3) Late parasitological failure (LPF; asymptomatic parasitemia on days 7–28 without previously meeting criteria for ETF or LCF); (4) Adequate clinical and parasitological response (ACPR; absence of parasitemia on day 28 without previously meeting criteria for ETF, LCF, or LPF).
- **Recrudescence** will be defined as the recurrence of asexual parasitemia within 28 days following antimalarial treatment comprising the same genotypes that caused the original illness. This is believed to result from incomplete clearance of asexual parasitemia because of inadequate or ineffective treatment.
- **Parasite clearance time**: time from first dose of ACT until first total and continued disappearance of asexual parasite forms.
- **Fever clearance time**: time from first dose until the first time the body temperature (for those with a raised temperature at enrolment) decrease to below 37.5°C and remain so for at least 24 hours.

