Translation of the informed consent to the local language: The informed consent has been translated to Yoruba (the local language) and is attached. Translation will has been verified for consistency and accuracy by an independent translator. The consent form will include the purpose of the study, risks and benefits to participants, confidentiality and voluntariness.

Beneficence to Enrollees: Enrollees in this study will have the advantage of been treated for malaria and any related febrile illnesses with no cost. Also, findings in the study will be useful in monitoring artemisinin resistance in Nigeria.

Non-maleficence to Enrollees: There is little or no risk involved in this study. Blood samples that will be collected from the prospective arm of the study will be via venipuncture technique which will be done by a qualified medical officer. The participant will only feel a mild pain and there may be a bruise which will go away in a few days.

Voluntariness: Enrollees in the study are absolutely free to decline or withdraw from the study without jeopardy and without loss of benefits to which they are entitled.

Summary of Activities

| ACTIVITY | Day 0 | Day 1 | Day 2 | Day 3 | Day 7 | Day 14 | Day 21 | Day 28 | Extra Visit | Extra Visit |
|---|-------|-------|-------|-------|-------|--------|--------|--------|-------------|-------------|
| Demographic data and clinical assessment | X | X | X | X | X | X | X | X | X | X |
| Blood smear – (Thick & Thin) | X | X | X | X | X | X | X | X | X | X |
| Blood spot on filter paper (for PCR) | X | X | X | X | X | X | X | X | X | X |
| Haematocrit | X | X | X | X | X | X | X | X | X | X |
| Full blood count | X | ✖ | ✖ | X | X | | | X | | |
| Blood Chemistry – Creatinine & Random Blood glucose | X | | | X | X | | | X | | |
| Liver Function test- AST, ALT, Bilirubin & Alkaline Phosphate | X | | | X | X | | | X | | |
| Adverse events recording | X | X | X | X | X | X | X | | | |
| Concomitant treatments recording | X | X | X | X | X | X | X | X | X | X |
| Study medications (AL or PA) | X | X | X | | | | | | | |

CASE RECORD FORM

**COMPARATIVE EFFICACY AND SAFETY OF PYRONARIDINE-
ARTESUNATE VERSUS ARTEMETHER-LUMEFANTRINE IN THE
TREATMENT OF Malaria AMONG CHILDREN IN SOUTH-WEST
NIGERIA**

PYRONARIDINE-ARTESUNATE VERSUS ARTEMETHER-LUMEFANTRINE STUDY

Study ID- PAAL:

Study ID: Hosp.No: Date of enrollment:

Sex: Age (months):

Date of birth/...../..... Weight (kg): Height (CM):

Temp (oC): Phone no:

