Address (+ brief description):
.....
.....
.....

Symptoms History

Record duration of symptoms in days (Today = 1) Fever: () Vomiting: () Chills & rigors ()

Diarrhoea: () Headache: () Abdominal pains: () Irritability: () Loss of appetite ()

Other complaint 1: Other complaint 2:

Past medical history:

History of drug allergy: (Yes/No) If yes, name of drug:

Any other relevant history 1:

Any other relevant history 2:

Treatment history: Has the child received any of the following drugs in the last 2 weeks (Yes/No)

CQ () SP () PCM () ACT () Specify.....

Antibiotic () Specify..... Other:

Clinical examination:

General: Palor (Yes/No) Icterus (Yes/No) Fever (Yes/No) Dehydration (Yes/No)

CVS: Pulse/min..... Apex Beat..... Heart sounds.....

Respiratory system: Resp. rate..... Breath sound.....

Abdomen: Liver size (Below costal margin)..... Spleen size..... Kidneys.....

Muscle tone: (1) Normal (2) Hypotonia (3) hypertonia Eyes: conjunctivitis/Discharge (Yes/No)

Ears: Discharge (Yes/No)

MP result: PCV.....

**PYRONARIDINE-ARTESUNATE VERSUS ARTEMETHER-
LUMEFANTRINE STUDY**

Study ID- PAAL:

Study ID -----

Study Drug Schedule

| Study Day | Date | Drug [PA or AL] Name of Drug | Dose | Time Drug Given |
|------------------|-------------|---|-------------|------------------------|
| Day 0 | | | 1st | |
| | | | 2nd | |
| Day 1 | | | 1st | |
| | | | 2nd | |
| Day 2 | | | 1st | |
| | | | 2nd | |

Comments:

Any vomiting? Yes/No

Time

Any Redosing?

Time

Any vomiting? Yes/No

Any other comments

CLINICAL FOLLOW UP RECORD

| | D0 | D1 | D2 | D3 | D7 | D14 | D21 | D28 | Day 35 | Day 42 | Other visit |
|---------------------------|-----------|-----------|-----------|-----------|-----------|------------|------------|------------|---------------|---------------|--------------------|
| Date | | | | | | | | | | | |
| Temp (°C) | | | | | | | | | | | |
| Pallor | | | | | | | | | | | |
| Jaundice | | | | | | | | | | | |
| HR/Pulse Rate | | | | | | | | | | | |
| Resp Rate | | | | | | | | | | | |
| Lung Fields | | | | | | | | | | | |
| Liver (cm) | | | | | | | | | | | |
| Spleen (cm) | | | | | | | | | | | |
| Weight (kg) | | | | | | | | | | | |
| PCV (%) | | | | | | | | | | | |
| Parasite Density/ μ L | | | | | | | | | | | |
| Gametocyte Count/ μ L | | | | | | | | | | | |

TREATMENT EMERGENT SIGNS AND SYMPTOMS (TESS)

| Features | Day 0 | | Day 1 | | Day 2 | | Day 3 | | Day 7 | | Day 14 | | Day 21 | | Day 28 | | Day 35 | | Day 42 | | Extra Visit | | Extra Visit | | |

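### The late-failure categories are not exhaustive: a symptomatic, afebrile recurrence fits neither, and if treated it can be scored ACPR under 3.7.2 but not under the Study Design definition

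*Combined protocol and SAP*

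**What the plan says.** The efficacy evaluation in 3.7.2 sorts children into four outcomes. The two late-failure rules are:

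- "Late clinical failure (LCF; danger signs or complicated malaria or fever and parasitemia on days 4–28", in a child with no earlier failure;
- "Late parasitological failure (LPF; asymptomatic parasitemia on days 7–28 without previously meeting criteria for ETF or LCF".

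ACPR in the same list requires a negative film on day 28 and no earlier ETF, LCF or LPF. It does not itself exclude parasitaemia found before day 28.

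Study Design (text numbered 3.2) allows only therapeutic failure or ACPR. It defines the primary outcome as PCR-adjusted ACPR, meaning "absence of patent parasitaemia, regardless of axillary temperature and without evidence of previous treatment failure up to day 28". ACPR without correction for reinfection is a secondary outcome.

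Two places deal with further treatment. Section 3.7.1 lifts the ban on other antimalarials when parasites recur, with no condition on symptoms or fever. Section 3.7.2 gives the alternative ACT to children who fail treatment.

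On films, 3.7 says "Thick blood film will be prepared from finger prick sample of each enrollee at each contact time", and 3.7.2 also describes thick smears only. The Summary of Activities lists thick and thin smears at every visit.

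**The concern.** A list of outcome categories has to place every child. This one leaves out the recurrence that comes with symptoms but without fever. The protocol can detect such children: 3.7.2 provides for evaluation on any day the child feels unwell and for a smear at every unscheduled visit, and the CRF records 16 named signs and symptoms other than fever.

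At stake is whether two readers of the protocol would give the same child the same primary or crude outcome. The trial is open label and the protocol does not define what counts as asymptomatic. Staff who know the treatment would therefore settle the category after seeing the child. Failures hidden at the same rate in both arms raise both cure rates and shrink the absolute difference, which favours a non-inferiority conclusion.

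**Working it through.** **Step 1: the categories.** Each parasitaemic presentation on days 7–28, with no earlier failure, read literally against 3.7.2:

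| Danger signs | Fever | Other symptoms | Category |
|---|---|---|---|
| Yes | Yes or no | Yes | LCF |
| No | Yes | Yes | LCF |
| No | No | No | LPF |
| No | No | Yes | none |

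One cell is empty. Two things can then happen to that child:

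- Still positive on day 28 in the same state: neither ACPR nor a failure. The CRF efficacy codes (ETF, LPF, LCF, ACPR, withdrawn, lost to follow-up) have no code for this.
- Treated under 3.7.1 and negative on day 28: ACPR by the wording of 3.7.2. Not ACPR under Study Design, which requires absence of patent parasitaemia whatever the temperature.

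Parasitaemia without fever or danger signs on days 4–6, which only an unscheduled visit could find, also has no late-failure category, because LPF starts on day 7.

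**Step 2: the plan's sample size.** Inputs from 3.6: cure 96.4% (AL) and 98.9% (PA), margin 5 points, power 90% or 80%.

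n = (z_α + z_β)² × [0.964×0.036 + 0.989×0.011] / [0.05 − (0.964 − 0.989)]² = (z_α + z_β)² × 0.045583 / 0.005625

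- z_α = 1.645: 69.3, so 70 (90% power); 50.0, rounded up to 51 (80% power). Both match the plan.
- z_α = 1.96, the value 3.6 lists: 85.1, so 86; 63.5, so 64. Neither matches.

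The plan's numbers therefore rest on a one-sided 0.05 test. Both values are carried below.

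**Step 3: weight of one child at 70 per arm.**

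- Expected failures: 70 × 0.036 = 2.5 (AL); 70 × 0.011 = 0.8 (PA).
- One child: 1/70 = 1.43 points, and 1.43/5 = 29% of the margin.

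Upper limit for AL minus PA cure, as difference + z × SE (Wald, in points):

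| AL failures | PA failures | Difference | SE | Limit, 1.645 | Limit, 1.96 |
|---|---|---|---|---|---|
| 2 | 3 | 1.43 | 3.13 | 6.6 | 7.6 |
| 2 | 2 | 0 | 2.82 | 4.6 | 5.5 |
| 3 | 3 | 0 | 3.42 | 5.6 | 6.7 |
| 3 | 2 | −1.43 | 3.13 | 3.7 | 4.7 |

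One uncounted PA failure takes the limit below 5 in both pairs with 1.645, and in the second pair with 1.96.

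**Step 4: effect on false non-inferiority, under assumptions.** Let a share s of failures in both arms fall in the empty cell and be scored as cure. The documents give no value for s. Take PA exactly at the margin (91.4% against 96.4%) and assume genotyping recovers none of these children. Observed failure rates are 0.036(1 − s) and 0.086(1 − s), the difference is d = 0.05(1 − s), and

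P(false non-inferiority) = Φ[(0.05 − d)/SE − z_α]

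| s | d | SE | z_α = 1.645 | z_α = 1.96 |
|---|---|---|---|---|
| 0 | 0.050 | 0.0402 | 5.0% | 2.5% |
| 10% | 0.045 | 0.0383 | 6.5% | 3.4% |
| 20% | 0.040 | 0.0363 | 8.5% | 4.6% |
| 40% | 0.030 | 0.0316 | 15.6% | 9.2% |

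The normal approximation is rough with so few failures.

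**The case against.** Several points on the other side are sound.

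- **Retreatment.** Section 3.7.2 gives the alternative ACT to children who fail treatment, so a child retreated under that sentence has already been judged a failure. The path to ACPR needs the broader permission in 3.7.1. A child not retreated would probably be caught later as LPF or LCF. This narrows the path but leaves the two sections in disagreement.
- **Genotyping.** A reader might infer that these recurrences will count as cures in the primary analysis. The documents do not support that. All recurrences by day 28 are to be genotyped, recrudescence is defined without any symptom condition, and Study Design already gives the stricter answer. What remains is that no text links a genotyping result to a category in 3.7.2.
- **Fever.** LCF gives no temperature threshold. If a history of fever counts, as it does at enrolment, the empty cell shrinks. It does not close.
- **Frequency.** The CRF symptom list might be read as showing that the case is common. It is a safety checklist that includes items such as rash and diplopia, and it says nothing about the share of recurrences that are symptomatic and afebrile.
- **Species.** LCF, LPF and ACPR name no species, so a reader might infer that other species would be counted as failures. That is a separate point, it adds failures rather than hiding them, and it is partly covered: mixed and other-species infections seen on microscopy are excluded at entry, density is defined on asexual parasites, gametocytes are recorded separately and thin films are scheduled.

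**Conclusion.** The point stands as a defect in an endpoint rule. Section 3.7.2 leaves one kind of late recurrence unclassified, and if that child is retreated and negative on day 28, it disagrees with Study Design about the outcome. The exposure is mainly in crude ACPR. It is less certain in the PCR-adjusted primary, where it depends on an unstated link between genotyping and category.

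The firm figure is the weight of one child: 1.4 points of a 5-point margin, with about 2.5 and 0.8 failures expected per 70. A reader might infer that the trial's false non-inferiority rate is 15.6%. The documents do not support that. For s of 10–40% the range is about 6.5–15.6% against 5%, or 3.4–9.2% against 2.5% with 1.96. Both ranges rest on an assumed s, PA exactly at the margin and no recovery through genotyping.

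**What to change.** 1. In 3.7.2, define LPF as any asexual *P. falciparum* parasitaemia on days 7–28 that does not meet ETF or LCF, whatever the other symptoms.
2. Define ACPR there, in line with Study Design, as no such parasitaemia through day 28 and no earlier failure.
3. State which category applies to parasitaemia without fever on days 4–6.
4. Reconcile 3.7.1 and 3.7.2 on when another antimalarial is given, so that every child treated for recurrence has a failure category. Which treatment rule applies is for the investigators to decide.
5. Make the film descriptions in 3.7 and 3.7.2 match the thick and thin smears in the Summary of Activities.

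The cost is a few sentences. The planned 70 per group does not change and no visit or sample is added, since both films are already scheduled. The reported failure rate may be slightly higher. The changes should be made before outcomes are known, because in an open-label trial a later choice of category could not be shown to be neutral.

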The artemisinins act by inhibiting *Plasmodium falciparum* encoded sarcoplasmic endoplasmic reticulum calcium ATPase. They inhibit development of gametocytes thus reducing transmission.[7] Gametocytes, the sexual stages of the malaria parasite, do not cause clinical disease but are vital to the maintenance of malaria transmission cycle. These gametocytes are present in symptomatic and asymptomatic parasitemic individuals.[7] The WHO defines artemisinin-based combination therapy for malaria as the simultaneous use of at least two efficacious schizonticidal drugs one of which is an artemisinin derivative. The two or more drugs must have different mechanisms of action and thus different biochemical targets in the parasite.[8] It is important that the two or more constituent drugs are efficacious and are used at individual full dosages. Artemisinin-based combination therapies (ACTs) are now the first-line treatment for acute uncomplicated malaria globally. They are more effective than the non-artemisinin-based combination or monotherapies, as they lead to rapid parasite clearance, hasten clinical recovery and reduce the chances of development of drug resistance in the parasite.[1]

Artemether-lumefantrine (AL) is the first fixed - dose ACT to be pre-qualified by the WHO and the most commonly used ACT as first-line drug for the treatment of uncomplicated falciparum malaria in sub-Saharan Africa.[6, 8]. It has also been extensively studied in Nigeria.[9-11] Artesunate-amodiaquine (ASAQ) the second most widely used ACT globally after artemether-lumefantrine is also currently used as a first line treatment in some countries in sub-Saharan Africa.[12-14] However, ASAQ is disadvantaged by the variability in dosing regimens between the different formulations of ASAQ.[15, 16] Dihydroartemisinin-piperaquine (DP) is another ACT that has been recommended by the WHO for use in the treatment of acute uncomplicated malaria.[17] However, DP is not widely used in sub-Saharan Africa compared to AL as its recommendation by the WHO is more recent.[1] Dihydroartemisinin-piperaquine has the advantage of daily dosing and does not require taking it with meal. The long half-life of piperaquine confers on DP a longer post treatment chemoprophylaxis when compared with AL.[18]

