2.1 SPECIFIC OBJECTIVES

1. Primary:

To determine the comparative efficacy of pyronaridine-artesunate and artemether-lumefantrine in the treatment of acute uncomplicated malaria in children in south-west Nigeria.

2. Secondary:

- i. To compare the efficacy and safety (crude – ACPR) of pyronaridine-artesunate and artemether-lumefantrine in the treatment of acute uncomplicated malaria in children in south-west Nigeria
- ii. To determine and compare the parasite clearance time and the fever clearance time of pyronaridine-artesunate and artemether-lumefantrine in the treatment of acute uncomplicated malaria in children in south-west Nigeria
- iii. To determine and compare gametocyte carriage between pyronaridine-artesunate and artemether-lumefantrine during treatment of acute uncomplicated malaria in children in south-west Nigeria
- iv. To compare the PCR Corrected cure rates of pyronaridine-artesunate and artemether-lumefantrine in the treatment of acute uncomplicated malaria in children in south-west Nigeria

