- **Gametocyte carriage**: proportions of patients with gametocyte at a given point in time using the Area Under the Curve Graph for PA will be compared with that of AL.

3.7.3 Safety parameters will be evaluated as follows:

- Safety will be analyzed in terms of adverse events and severe adverse events using clinical signs, symptoms and laboratory parameters.
- Liver enzymes (ALT/AST) >3 times upper limit of normal (ULN) plus peak total bilirubin >2 times ULN in the absence of a significant alkaline phosphatase increase (= Hy's law) will be deemed as serious adverse effects (SAE).
- ALT and AST >5 times ULN will be deemed an AESI. (see below)

Serious Adverse Events

An adverse event will be considered serious if it fulfils one of the following criteria:

- causes death or
- is life-threatening or necessitates hospitalization or prolongs hospitalization or results in persistent or significant disability/incapacity or is a medically important event constitutes a possible Hy's Law

An example of an important medical event is one that while not-immediately life-threatening might become so if there had been no intervention

In case of SAEs, independent of causality, the healthcare personnel must immediately contact the PI / Investigator for validation of the seriousness and determination of the causality.

Subsequently, the procedure described below must be followed:

- SEND (within 24 hours and pdf scanned documents) the signed and dated copy of the “Adverse Event form” and the form “SAE complementary information” to Shin Poong Pharmacovigilance (PV) (Tel/[contact] or email: [contact])
- Contact immediately (the same day) the medical monitor/Pyramax QPPV responsible for safety in case of death or life-threatening events.
- The follow-up of each fatal or life-threatening AE must be provided to the medical monitor and Shin Poong PV within the same timeline as the initial report (within 24 hours and preferably by email).
- ATTACH to the Case Record Form (CRF) the photocopy of all available results and examinations which were undertaken (and their date). Analysis results must be accompanied by the laboratory normal ranges. Special consideration shall be taken to ensure patient anonymity, and to the correct completion of the patient’s study specific identifier in the copies of the source documents provided to the sponsor.

Causality

All adverse events must have causality assigned by the investigator. As a guide causality can be assigned as follows:

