3.7.5 Follow-up of Adverse Events

The healthcare personnel must take all appropriate measures to protect the safety of the patients. Personnel must ensure to document follow-up of the evolution of each adverse event (clinical, biological or other) until resolution or until the stabilization of the patient's status.

All new relevant information concerning the initial SAE shall be recorded on a form "SAE follow-up information form" by the nursing staff of the health centre, and shall be validated by the PI/co-PI who shall transfer the form to the local person/physician responsible for the pharmacovigilance of the project and Shin Poong PV.

In case of a serious adverse event the patient must be followed until complete resolution and normalization of all analysis results, or until chronicity of the patient's status. This can imply that the follow-up of the patient must continue beyond the period of follow-up per protocol, and that additional investigations could be requested.

DATA ANALYSIS.

Data will be entered into the computer using the Epi-data software. This subsequently would be cleaned and transferred to SPSS Statistic Software version 20 for analysis. The outcome of interest (dependent variable) presented as a categorical variable with, presence of malarial parasitemia, and the level of efficacy reported. The independent or explanatory variable of interest in this study would be use of chemotherapy. All independent variable would be reported as categorical. Proportions of treatment outcome will be compared by using chi square. Normally distributed continuous data will be compared using unpaired student t-test. Mean values will be given as mean \pm SD and values of $P < 0.05$ will be considered statistically significant.

ETHICAL CONSIDERATIONS

This study, will be a prospective randomized open label clinical trial comparing the safety and efficacy of Pyronaridine-artesunate and Artemether-lumefantrine in the treatment of symptomatic acute uncomplicated malaria in Nigerian children aged 3 to 144 months who seek treatment in the study hospital. The studies will be conducted according to Good Clinical Practice and the Declaration of Helsinki.

Confidentiality of data: Personal details of enrollees in the study will be treated with utmost confidentiality, as it is against the principles of good clinical practice to make such information public. Also, codes will be assigned to all participants.

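### The gametocyte comparison ignores the Day 0 gametocyte status already recorded, which can cost precision and leaves it exposed to chance baseline imbalance

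*Combined protocol and SAP*

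**What the plan says.** Section 2.1 lists as secondary objective iii: "To determine and compare gametocyte carriage between pyronaridine-artesunate and artemether-lumefantrine during treatment". Section 3.7.2 gives the only definition of the measure: "proportions of patients with gametocyte at a given point in time using the Area Under the Curve Graph for PA will be compared", the comparator being AL. It does not mention status at enrolment.

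The Data Analysis section assigns no test to gametocytes by name. It says "Proportions of treatment outcome will be compared by using chi square" and "Normally distributed continuous data will be compared using unpaired student t-test". Neither test is adjusted or stratified. Section 3.2 describes randomisation only as a pre-generated code, with no stratification factor.

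The baseline value is nevertheless collected. Section 3.7 says "Gametocyte carriage will be specifically looked out for in the thick film on all contact days", and the clinical follow-up record in the case record form has a "Gametocyte Count" row with a D0 column. The background section notes of gametocytes: "These gametocytes are present in symptomatic and asymptomatic parasitemic individuals". It also says that artemisinins inhibit gametocyte development.

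**The concern.** A child positive after treatment may have enrolled with gametocytes that have not yet cleared, or may have developed them since. A pooled proportion adds the two together. It therefore depends partly on how many Day 0 carriers happened to fall in each arm, which has nothing to do with the drugs. When Day 0 status predicts later status, leaving it out adds noise to the comparison.

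At stake is how informative the answer to secondary objective iii is. There is also a practical risk. If an imbalance is seen at the end and adjusted for then, the adjustment is open to the charge of being post hoc. The plan already conditions on baseline for a neighbouring outcome: section 3.7.2 limits fever clearance time to children febrile at enrolment.

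**Working it through.** **Inputs from the documents.** Section 3.6 gives 70 evaluable per group and 84 enrolled per group. The 70 reproduces from the plan's formula with a one-sided 5% deviate: (1.645 + 1.28)² × (0.964 × 0.036 + 0.989 × 0.011) / 0.075² = 69.3, rounded up to 70. It is used here only as the number of children available. No power is stated for gametocytes.

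**Assumptions, because the documents give no rates.** Day 0 carriage is 2% to 20%. Persistence, meaning the share of Day 0 carriers still positive on Day 7 under AL, is 30% to 70%. Under AL, 2% of Day 0 non-carriers are positive on Day 7. PA multiplies both risks by 0.3. Tests are two-sided at 5%.

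**Step 1: what the pooled proportion contains.** Under AL it is carriage × persistence + (1 − carriage) × 0.02.
- 10% carriage, 70% persistence: 0.070 + 0.018 = 0.088, of which 80% is carry-over.
- 10% carriage, 30% persistence: 0.030 + 0.018 = 0.048, of which 62.5% is carry-over.
- 2% carriage, 70% persistence: 0.014 + 0.0196 = 0.0336, of which 42% is carry-over.

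**Step 2: chance imbalance at Day 0.** The SD of the between-arm difference is √(2p(1 − p)/n). At p = 0.10 this is √(0.18/84) = 4.6 points, or √(0.18/70) = 5.1 points. From the exact binomial distribution, a gap of 5 points or more arises in about 25% of trials at 84 per arm and 32% at 70 per arm.

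**Step 3: what a gap does when the drugs do not differ.** At 70% persistence, a 5-point gap shifts the expected Day 7 difference by 5 × (0.70 − 0.02) = 3.4 points. The standard error of that difference at 84 per arm is √(2 × 0.088 × 0.912/84) = 4.4 points. In simulated null trials (84 per arm, 10% carriage, 70% persistence), overall type I error is about 5% for the pooled and the stratified test. Within the quarter of trials with a gap of 5 points or more, the pooled test is falsely positive about 15% of the time, against about 5% when stratified.

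**Step 4: power at 70 per arm.** This compares a pooled chi-square with a Cochran-Mantel-Haenszel test stratified by Day 0 status, both without continuity correction, by simulation.

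| Day 0 carriage | Persistence | Pooled | Stratified |
|---|---|---|---|
| 2% | 70% | 11% | 9.5% |
| 10% | 30% | 18% | 19% |
| 10% | 50% | 26% | 32% |
| 10% | 70% | 35% | 48% |
| 20% | 70% | 60% | 77% |

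If all 84 enrolled per arm were evaluable, the 10% carriage, 70% persistence row would read 38% and 55%.

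**Step 5: a different effect model.** Suppose the arms differ only in new appearance (15% under PA against 3% under AL among Day 0 non-carriers), with equal persistence. At 70 per arm and 10% carriage, power moves from 48% to 55% at 50% persistence and from 40% to 63% at 90% persistence. The gain is not peculiar to the first model.

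**Step 6: continuity correction.** At 10% carriage and 70% persistence under the first model, a continuity-corrected Mantel-Haenszel test has power of 27.5% at 70 per arm and 36.5% at 84. Both are below the pooled test, at 35% and 38%, so the gain disappears.

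**The case against.** The strongest objection is that nothing is broken. Overall carriage is a legitimate target: objective iii asks for it, and the background section ties gametocytes to transmission. Randomisation keeps the unadjusted comparison valid. This stands, and it is why the overall comparison should be kept.

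Two stronger readings are tempting, and the documents support neither.
- A reader might infer that a Day 0 imbalance will be reported as a drug difference. Overall type I error stays near 5%. Even among null trials with a gap of 5 points or more, about 85% of pooled tests are correctly negative.
- A reader might infer that first-week carriage is mostly carry-over. The documents give no frequency at Day 0 and no persistence. Step 1 shows that the share runs from 42% to 80% across the assumed settings.

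It is also fair to say that the pooled chi-square is inferred. The plan names it for treatment outcomes, and section 3.7.2 refers to an area under the curve without saying how that is tested. No baseline adjustment appears under either reading. The gain is negligible in some settings and slightly negative at 2% carriage, and power stays low in most rows of the table. A stratified test still merges clearance and prevention into one statistic, so only a table by Day 0 status separates them. Repeating the test at each visit would raise a multiplicity problem. The fix below takes account of these limits.

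**Conclusion.** The concern holds as one of efficiency and robustness to chance imbalance, not of bias. The plan leaves a recorded baseline value unused in a named secondary comparison. Across the settings tabulated at 70 evaluable per arm, stratifying changes power by between −1.5 points (2% carriage) and +17 points (20% carriage, 70% persistence). The gain depends on Day 0 carriage and persistence both being appreciable, and on using the uncorrected test. All rates are assumptions. The false-positive figure of about 15% applies only to null trials with a Day 0 gap of 5 points or more, at 10% carriage and 70% persistence with 84 per arm. The primary PCR-adjusted ACPR comparison is untouched. This is a cheap improvement worth making before the data are seen.

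**What to change.** Keep the overall PA against AL comparison and add to the Data Analysis section:
- Name one post-treatment visit, for example Day 7, as the main gametocyte comparison.
- Analyse it with a Cochran-Mantel-Haenszel test without continuity correction, stratified by Day 0 gametocyte status (present or absent). State the version explicitly and check which one the software reports.
- Treat the other visits as descriptive.
- Tabulate by arm clearance among Day 0 carriers and new appearance among Day 0 non-carriers.

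The cost is wording and a little analysis work, with no new samples, visits or patients. There are two downsides. Up to about 2 points of power may be lost if Day 0 carriage is very low. The clearance table will be thin: at 10% carriage it rests on 0.10 × 70 = 7 to 0.10 × 84 = 8.4 children per arm, so it should be read as description only.
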